14.1.2 EYE DRYNESS SCORE AS THE PRIMARY ANALYSIS

Eye dryness will be assessed pre-treatment at Visit 1, pre-CAE at Visit 2, and every 5 minutes during CAE® exposure at Visit 2. For each assessment, the participant will be asked to rate their ocular symptoms (both eyes simultaneously) due to eye dryness by placing a vertical mark on a 100 mm horizontal line to indicate the level of discomfort; 0 corresponds to "no discomfort" and 100 corresponds to "maximal discomfort".

Treatment with study drug will be administered upon the participant reporting an Ocular Discomfort ([REDACTED] Scale) score ≥ 3 at two or more consecutive timepoints in at least one eye during CAE® exposure. If a participant has an Ocular Discomfort rating of 3 at time = 0 for an eye, s/he must report an Ocular Discomfort rating of 4 for two consecutive measurements for that eye. Participant will resume symptom assessments 1 minute after the application ends every five minutes.

The primary analysis will be a one-timepoint analysis in which the pre-treatment EDS will be the EDS at the timepoint that the subject first qualifies for study drug administration during the CAE® and post-treatment EDS will be the EDS at the first timepoint following qualification. If a participant fails to qualify

for study drug administration, the timepoint of qualification and the pre-treatment and post-treatment EDS will be missing.

Eye dryness score will be summarized by visit, timepoint, and treatment with quantitative descriptive statistics (n, mean, median, standard deviation, minimum and maximum).

The change in EDS from pre- to post-treatment will be analyzed using an [REDACTED] model with pre-treatment EDS and timepoint of qualification for study drug administration as covariates and with treatment as a fixed effect. LS means for each treatment, the corresponding 95% CIs, and the estimated treatment difference between each dose of OC-02 Nasal Spray and placebo will be calculated from this [REDACTED] model. A study site by treatment interaction will also be explored in a separate model to evaluate how the treatment effect may differ across study sites. In the case of a significant interaction at the 0.05 level, analyses will be performed by site to understand how the treatment effect differs across sites. The differences in means, two-sided 95% confidence intervals (CI) for the difference in means and p-values will be reported. Pairwise t-tests from the [REDACTED] model will be used to compare treatment and placebo groups.

The primary analyses will be performed on the ITT population on observed data only. SAS code for the [REDACTED] analysis will resemble the SAS code for Schirmer's test. [REDACTED] analysis estimates of pre- to post-treatment changes will be displayed in a bar chart with standard error bars by treatment group. Two sample t-tests and non-parametric Wilcoxon rank sum tests will be used to compare treatments as unadjusted sensitivity analyses. Sensitivity analyses will also be performed on the ITT population using MCMC to impute missing data, as well as the PP population with observed data only.

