5.1 Method of Assigning Subjects to Treatment Groups

Each subject who qualifies will be assigned a screening number. All screening numbers will be assigned in strict numerical sequence at a site and no numbers will be skipped or omitted. If all inclusion and exclusion criteria are met at Visit 1, each qualifying subject will then be assigned a randomization number.

A randomization schedule will be provided to each investigational site. The randomization schedule will be stratified by site, such that there will be an approximate equal number of subjects assigned to each of the four treatment arms at each site. The site staff will dispense to the patient the study kit labeled with the corresponding randomization number. The randomization number will be recorded on the patient's source document and electronic case report form (eCRF). The Sponsor, Investigators, and study staff will be masked during the randomization process and throughout the study.

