14.2.1 EYE DRYNESS SCORE

Change from pre- to post-treatment in EDS will be analyzed at each individual timepoint (based on the timepoint from the pre-treatment assessment to the respective post-treatment assessment) in a manner similar to the primary analysis for EDS given in section 14.1.2. ANCOVA models will be used that include pre-treatment EDS, timepoint of qualification, treatment and study site as covariates. ANCOVA analysis estimates of pre- to post-treatment changes will be displayed graphically by timepoint in a line plot by treatment group. Two sample t-tests and non-parametric Wilcoxon rank sum tests will be used to compare treatments as unadjusted sensitivity analyses.

The change from pre- to post-treatment in EDS will also be analyzed in a three-timepoint analysis by subtracting for each subject the average EDS at the three timepoints following the timepoint of qualification (post-treatment average) from the average EDS at the three most recent timepoints at or prior to the timepoint of qualification (pre-treatment average). This pre- to post-treatment average change in EDS will be analyzed using an ANCOVA model with pre-treatment average EDS and timepoint of qualification for study drug administration as covariates and with treatment as a fixed effect. LS means for each treatment, the corresponding 95% CIs, and the estimated treatment difference between each dose of OC-02 Nasal Spray and placebo will be calculated from this ANCOVA model. ANCOVA analysis estimates of pre- to post-treatment average change will be displayed in a bar chart with standard error bars by treatment group. The differences in means, two-sided 95% confidence

intervals (CI) for the difference in means and p-values will be reported. Pairwise t-tests from the [REDACTED] model will be used to compare treatment and placebo groups.

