A [REDACTED] model will also be used as an additional analysis of change from pre- to post-treatment in EDS. This model will include site, treatment, timepoint, and the interaction between treatment and timepoint as fixed effects, and subject as a random effect. This model will also include a fixed effect for the duration between a post-treatment timepoint and the timepoint of qualification, and the interaction of this duration variable with treatment. The duration variable will be defined as zero for all pre-treatment timepoints and durations greater than 60 minutes will be pooled together. Thus the variable will be treated as discrete, with possible values 0 minutes, 5 minutes, ..., 60 minutes, and 60+ minutes. An unstructured covariance matrix will initially be used to model the covariance among repeated measures; however, if the model fails to converge using this covariance structure, either heterogeneous TOEPLITZ, homogeneous TOEPLITZ, or compound symmetry will be implemented according to the Akaike information criterion with a correction for finite sample sizes (AICc).

[REDACTED]

[REDACTED]

[REDACTED]

[REDACTED]

[REDACTED]

[figure not shown]
RU

Estimates of pre- to post-treatment changes will be displayed graphically by duration in a line plot by treatment group.

14.2.2 [REDACTED] OCULAR DISCOMFORT SCALE

Ocular discomfort scores will be subjectively graded by the subjects using the [REDACTED] Ocular Discomfort Scale at pre-treatment Visit 1 and at various timepoints during the CAE® exposure at Visit 2, immediately upon entering the chamber and every 5 minutes thereafter for the duration of the 120 minute exposure. The ocular discomfort scale ranges from 0 to 4 where 0 = no discomfort, 1 = intermittent awareness, 2 = constant awareness, 3 = intermittent discomfort, and 4 = constant discomfort.

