[REDACTED] Ocular Discomfort Scale results will be summarized by timepoint at Visit 2 and treatment with quantitative descriptive statistics. Change from pre- to post-treatment in [REDACTED] Ocular Discomfort Scale results will also be summarized by timepoint (based on the timepoint from the pre-treatment assessment to the respective post-treatment assessment) at Visit 2 and treatment group with quantitative descriptive statistics in a manner similar to EDS. [REDACTED] models will be used that include pre-treatment ocular discomfort, timepoint of qualification, treatment and study site as covariates. [REDACTED] analysis estimates of pre- to post-treatment changes will be displayed graphically by timepoint

in a line plot by treatment group. Two sample t-tests and non-parametric Wilcoxon rank sum tests will be used to compare treatments as unadjusted sensitivity analyses.

15. Safety Analyses

All safety analyses will be conducted using the Safety population.

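### As written, the primary one-timepoint and the three-timepoint EDS models omit study site, the randomization stratum, so their standard errors may be slightly too large

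*SAP*

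**What the plan says.** SAP 5.1 (and Protocol 8.1.5 in the same terms) sets the allocation: "The randomization schedule will be stratified by site, such that there will be an approximate equal number of subjects" in each of the four arms at each site. Protocol 5.1 plans up to 3 sites.

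The legible model terms are as follows.

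- **Primary one-timepoint EDS (SAP 14.1.2):** "pre-treatment EDS and timepoint of qualification for study drug administration as covariates and with treatment as a fixed effect". Site enters only through a separate exploratory site-by-treatment interaction model, with by-site analyses if that interaction is significant.
- **Three-timepoint EDS (SAP 14.2.1):** "ANCOVA model with pre-treatment average EDS and timepoint of qualification for study drug administration as covariates and with treatment as a fixed effect". No site.
- **Per-timepoint EDS (SAP 14.2.1):** "ANCOVA models will be used that include pre-treatment EDS, timepoint of qualification, treatment and study site as covariates".
- **Repeated-measures EDS (SAP 14.2.1):** "This model will include site, treatment, timepoint, and the interaction between treatment and timepoint as fixed effects, and subject as a random effect".
- **Ocular discomfort (SAP 14.2.2):** "models will be used that include pre-treatment ocular discomfort, timepoint of qualification, treatment and study site as covariates".
- **Schirmer's test, the other primary endpoint (SAP 14.1.1):** baseline Schirmer and study site are the covariates.

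The protocol synopsis has the same pattern: site is in its Schirmer and per-timepoint EDS models and absent from its primary EDS model. The omission is therefore not an undisclosed change. SAP Section 18 records that the primary EDS analysis was rewritten and that timepoint of qualification was added to the EDS and discomfort analyses. It does not mention site.

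Two further statements in SAP 14.1.2 matter. The EDS "analysis will resemble the SAS code for" Schirmer's test, and that code is redacted. For a subject who never qualifies for dosing in the chamber, "the timepoint of qualification and the pre-treatment and post-treatment EDS will be missing".

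**The concern.** Stratifying by site makes the arms nearly balanced on site, so the true sampling variance of the treatment difference excludes almost all between-site variance. A model without site does not know this. It leaves that variance in the residual and reports a standard error larger than the estimate's real variability. Confidence intervals are then too wide, the test rejects less often than 5% under the null, and some power is lost. Including the stratum removes the mismatch.

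There is also an inconsistency within one endpoint. The per-timepoint EDS models are described as similar to the primary EDS analysis, yet they carry site. Read literally, the model at the first post-treatment timepoint has the primary outcome and the primary covariates plus site. Tables 14.2.2.1 and 14.2.3.1 would then show two estimates, intervals and p-values for the same contrast, with no reason given for the difference.

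**Working it through.** **Inputs from the documents.** About 160 subjects, 40 per arm, four arms, 5% dropout (Protocol 10.3); up to 3 sites (Protocol 5.1); two-sided 0.05 (SAP 9.4). The one figure that can be reproduced is the number of completers: 40 × 0.95 = 38 per arm, as stated. No legible passage gives an EDS effect size, SD or power, so there is no power figure to reproduce; the text of SAP Section 6 is redacted.

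**Inputs assumed.** The share ρ of residual EDS-change variance explained by site, and the proportion of subjects with EDS data. The documents give neither.

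**Closed form, nearly all subjects with EDS data.**

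- Reported SE without site ÷ with site = 1/√(1−ρ)
- Actual alpha without site = 2·[1−Φ(1.96/√(1−ρ))]
- Power without site, if it is 80% with site = 1−Φ(1.96/√(1−ρ) − 2.80)
- Gap between highest and lowest site, for three equal and evenly spaced sites = √(6ρ/(1−ρ)) within-site SD

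| ρ | SE ratio | Alpha | Power | Site gap (SD) |
|---|---|---|---|---|
| 2% | 1/√0.98 = 1.010 | 0.048 | 79.4% | 0.35 |
| 5% | 1/√0.95 = 1.026 | 0.044 | 78.5% | 0.56 |
| 10% | 1/√0.90 = 1.054 | 0.039 | 76.9% | 0.82 |

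The last column shows what each share demands. The endpoint is a within-subject change, so the lower shares are more plausible.

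**Simulation, allowing for non-qualifiers.** There were 60,000 trials per cell (Monte Carlo SE for alpha about 0.0009). Each had 160 randomized at sites of 56/52/52, in permuted blocks of 4 (assumed). ANCOVA on pre-treatment EDS and timepoint of qualification was fitted without and with site. EDS data were missing at random, regardless of arm and site (assumed). The effect was set to give about 79% power with site. Entries are for 100 / 95 / 70 / 50% of subjects with EDS data.

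| ρ | SE ratio, without ÷ with site | Alpha without site | Power gained by adding site (points) |
|---|---|---|---|
| 0% | 1.000 / 1.000 / 0.997 / 0.993 | not tabulated | 0.0 / 0.0 / −0.2 / −0.7 |
| 2% | 1.010 / 1.010 / 1.008 / 1.003 | 0.047 / 0.047 / 0.048 / 0.049 | 0.6 / 0.5 / 0.3 / 0.1 |
| 5% | 1.027 / 1.027 / 1.024 / 1.020 | 0.046 / 0.046 / 0.045 / 0.047 | 1.5 / 1.7 / 1.5 / 1.4 |
| 10% | 1.056 / 1.056 / 1.053 / 1.048 | 0.038 / 0.038 / 0.042 / 0.044 | 3.3 / 3.4 / 3.4 / 3.2 |

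With site in the model, alpha was 0.049 to 0.051 throughout. A second, separately written simulation (38 per arm, 6,000 null trials) gave SE ratios of 1.010, 1.027 and 1.055 and alphas of 0.047, 0.046 and 0.038 at the same three shares.

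**What the SE ratio consists of, at ρ = 10%.**

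- All subjects with data: the mean reported SE without site is 0.2373 and the true SD of that estimate is 0.2257, so it is 0.2373/0.2257 = 1.051 times too large. The true SD with site is 0.2255, so almost no real precision is lost.
- Half with data: 0.3415/0.3343 = 1.022, so the reported SE is about 2% too large. The true SD with site is 0.3260, and 0.3343/0.3260 = 1.025, so the estimate without site is also about 2.5% less precise. Random loss of subjects has partly undone the site balance.

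**The case against.** Five points can be made for leaving the plan alone.

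1. *The redacted code may already contain site.* It is said to follow the Schirmer code, and the Schirmer model has site. This stands as a limit: the point is about the written text. If the code contains site, text and code disagree and the text must be corrected; if it does not, both need the term.
2. *A site-adjusted version is already planned.* The per-timepoint model at the first post-treatment timepoint appears to be exactly that, in ITT and PP. This also stands, and it lowers the stakes for the one-timepoint analysis. It does not supply the result labelled primary, and the three-timepoint model has no such counterpart.
3. *No harm is shown.* The documents give no site effect, and the error is conservative. At shares of 2% to 5% the gain is only 0.1 to 1.7 power points, and if site has no effect the change costs up to 0.7 point. SAP 3.4 calls the hypotheses exploratory, and Protocol 10.3 does not base the sample size on power. All true; these facts settle the severity, not whether the term belongs in the model.
4. *The excess nearly vanishes if many subjects do not qualify.* With half the subjects contributing, a further run of 20,000 trials per cell gave reported SE against true SD of 0.3267 vs 0.3288 at 2%, 0.3318 vs 0.3303 at 5% and 0.3413 vs 0.3362 at 10%: no excess, about 0.5% and about 1.5%. This is a fair qualification. What adding site then recovers is mainly real precision.
5. *Omitting a stratification factor is valid, and the protocol did the same.* It is valid in that type I error is not inflated, and nothing was concealed. It is still less efficient than the SAP's own practice in its other models.

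**Conclusion.** The concern holds, at low severity. The legible term lists of two EDS models, one of them primary, omit the randomization stratum that the SAP's other efficacy models include. If site explains 2% to 10% of residual EDS-change variance and nearly all subjects have EDS data, the reported standard error is about 1% to 5.5% too large, alpha falls to between 0.048 and 0.038, and 0.5 to 3.4 power points are lost. If site has no effect, nothing is lost. If many subjects fail to qualify, the excess in the standard error shrinks, although at shares of 5% and 10% adding site still gains 1.4 and 3.2 points with half the subjects contributing. These sizes rest on an assumed site share, an assumed qualification rate, and missingness unrelated to arm and site. The finding that the text omits site rests on none of these.

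**What to change.** Add study site as a fixed effect to the primary one-timepoint EDS model in SAP 14.1.2, to the three-timepoint EDS model in SAP 14.2.1, and to the analysis model applied to the imputed EDS data sets. Check that the imputation model carries site as well, so that the two match. Confirm that the code agrees with the revised text.

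The cost is one model term and at most 2 degrees of freedom. With an intercept, three treatment terms, two covariates and two site terms (8 parameters), the residual degrees of freedom are 160 − 8 = 152, 152 − 8 = 144, 112 − 8 = 104 or 80 − 8 = 72 if 100, 95, 70 or 50% of subjects have EDS data. No new data are needed. The work is a change of SAP wording, plus the code if it does not already contain the term.

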14.2 Other Efficacy Analyses

The continuous variables for the other efficacy analyses will be summarized descriptively (n, mean, standard deviation, median, min and max) at the pre-treatment at Visit 1 and by timepoint during the CAE[®] exposure at Visit 2. Changes from pre- to post-treatment will also be summarized descriptively by timepoint (based on the change in timepoint from the pre-treatment assessment to the respective post-treatment assessment) at Visit 2 and treatment group. No imputation will be performed for secondary efficacy variables. Analyses will be performed on the ITT and PP populations with observed data only. All exploratory measures will also be presented in subject listings.

The following secondary efficacy endpoints will be tested:

- Eye Dryness Score throughout CAE[®]
- Ora Calibra[®] Ocular Discomfort Scale;

14.2.1 EYE DRYNESS SCORE

Change from pre- to post-treatment in EDS will be analyzed at each individual timepoint (based on the timepoint from the pre-treatment assessment to the respective post-treatment assessment) in a manner similar to the primary analysis for EDS given in section 14.1.2. ANCOVA models will be used that include pre-treatment EDS, timepoint of qualification, treatment and study site as covariates. ANCOVA analysis estimates of pre- to post-treatment changes will be displayed graphically by timepoint in a line plot by treatment group. Two sample t-tests and non-parametric Wilcoxon rank sum tests will be used to compare treatments as unadjusted sensitivity analyses.

The change from pre- to post-treatment in EDS will also be analyzed in a three-timepoint analysis by subtracting for each subject the average EDS at the three timepoints following the timepoint of qualification (post-treatment average) from the average EDS at the three most recent timepoints at or prior to the timepoint of qualification (pre-treatment average). This pre- to post-treatment average change in EDS will be analyzed using an ANCOVA model with pre-treatment average EDS and timepoint of qualification for study drug administration as covariates and with treatment as a fixed effect. LS means for each treatment, the corresponding 95% CIs, and the estimated treatment difference between each dose of OC-02 Nasal Spray and placebo will be calculated from this ANCOVA model. ANCOVA analysis estimates of pre- to post-treatment average change will be displayed in a bar chart with standard error bars by treatment group. The differences in means, two-sided 95% confidence

intervals (CI) for the difference in means and p-values will be reported. Pairwise t-tests from the [REDACTED] model will be used to compare treatment and placebo groups.

A [REDACTED] model will also be used as an additional analysis of change from pre- to post-treatment in EDS. This model will include site, treatment, timepoint, and the interaction between treatment and timepoint as fixed effects, and subject as a random effect. This model will also include a fixed effect for the duration between a post-treatment timepoint and the timepoint of qualification, and the interaction of this duration variable with treatment. The duration variable will be defined as zero for all pre-treatment timepoints and durations greater than 60 minutes will be pooled together. Thus the variable will be treated as discrete, with possible values 0 minutes, 5 minutes, ..., 60 minutes, and 60+ minutes. An unstructured covariance matrix will initially be used to model the covariance among repeated measures; however, if the model fails to converge using this covariance structure, either heterogeneous TOEPLITZ, homogeneous TOEPLITZ, or compound symmetry will be implemented according to the Akaike information criterion with a correction for finite sample sizes (AICc).

[REDACTED]

[REDACTED]

[REDACTED]

[REDACTED]

[REDACTED]

[figure not shown]
RU

Estimates of pre- to post-treatment changes will be displayed graphically by duration in a line plot by treatment group.

14.2.2 [REDACTED] OCULAR DISCOMFORT SCALE

Ocular discomfort scores will be subjectively graded by the subjects using the [REDACTED] Ocular Discomfort Scale at pre-treatment Visit 1 and at various timepoints during the CAE® exposure at Visit 2, immediately upon entering the chamber and every 5 minutes thereafter for the duration of the 120 minute exposure. The ocular discomfort scale ranges from 0 to 4 where 0 = no discomfort, 1 = intermittent awareness, 2 = constant awareness, 3 = intermittent discomfort, and 4 = constant discomfort.

[REDACTED] Ocular Discomfort Scale results will be summarized by timepoint at Visit 2 and treatment with quantitative descriptive statistics. Change from pre- to post-treatment in [REDACTED] Ocular Discomfort Scale results will also be summarized by timepoint (based on the timepoint from the pre-treatment assessment to the respective post-treatment assessment) at Visit 2 and treatment group with quantitative descriptive statistics in a manner similar to EDS. [REDACTED] models will be used that include pre-treatment ocular discomfort, timepoint of qualification, treatment and study site as covariates. [REDACTED] analysis estimates of pre- to post-treatment changes will be displayed graphically by timepoint

in a line plot by treatment group. Two sample t-tests and non-parametric Wilcoxon rank sum tests will be used to compare treatments as unadjusted sensitivity analyses.

15. Safety Analyses

All safety analyses will be conducted using the Safety population.

